### 7.1. Adverse Events

The verbatim terms used in the CRF by investigators to identify adverse events will be coded using the Medical Dictionary for Regulatory Activities (MedDRA). Any AE occurring at or after the initial administration of study agent through the end of the trial is considered to be treatment emergent. If the event occurs on the day of the initial administration of study agent, and either event time or time of administration are missing, then the event will be assumed to be treatment emergent. If the event date is recorded as partial or completely missing, then the event will be considered to be treatment emergent unless it is known to be prior to the first administration of study agent based on partial onset date or resolution date. All reported treatment-emergent adverse events will be included in the analysis. For each adverse event, the number and percentage of subjects who experience at least 1 occurrence of the given event will be summarized by treatment group.

Summary tables will be provided for:

- AEs
- Serious AEs (SAEs)
- AEs leading to discontinuation of study agent
- AEs by severity
- AEs by relationship to study agent
- Infections
- Serious infections
- Infections treated with oral or parenteral antimicrobial treatment
- Injection-site reactions
- AEs of psoriasis

In addition to the summary tables, listings will be provided for subjects who:

- Had SAEs
- Had AEs leading to discontinuation of study agent
- AEs of severe intensity
- Serum sickness-like reactions and anaphylactic reactions

In addition, a listing will be provided of all AEs that occurred after Week 16 for subjects who were randomized to placebo at Week 0 and were not crossed over to receive guselkumab.

Any unfavorable or unintended sign that occurs at the injection site is an injection site reaction and will be recorded as an injection site reaction by the investigator on the eCRF. An infection is defined as any AE that was recorded as an infection by the investigator on the eCRF.

The treatment-emergent adverse events of psoriasis include any event of erythrodermic psoriasis, pustular psoriasis, guttate psoriasis, inverse psoriasis, palmo-plantar psoriasis and worsening or exacerbation of psoriasis. Frequency of these events will be summarized.

Since safety should be assessed relative to exposure and follow-up, most AE summary tables will include average weeks of follow-up and average number of study agent administrations for each treatment group.

## 7.2. Clinical Laboratory Tests

All clinical laboratory reports will be displayed for the subjects included in the safety analysis set. The clinical laboratory parameters to be evaluated by the central laboratory include but are not limited to:

- **Hematology:** hemoglobin, hematocrit, lymphocytes, neutrophils, platelets, red blood cell (RBC) count and white blood cell (WBC) count.
- **Chemistry:** albumin, alkaline phosphatase, alanine aminotransferase, aspartate aminotransferase, total carbon dioxide (CO2), total bilirubin, blood urea nitrogen/urea, calcium, chloride, creatinine, glucose, potassium, total protein, sodium.

Box plots of laboratory measurements and change from baseline will be provided for selected laboratory analytes.

Applicable laboratory results will be graded according to National Cancer Institute's Common Terminology Criteria for Adverse Events (NCI-CTCAE version 4.03). The worst NCI-CTCAE will be summarized by treatment group.

For nonfasting glucose, the screening measurement will be used as the baseline measurement. A listing of subjects with 1 or more NCI-CTCAE toxicity grade  $\geq 2$  abnormalities in hematology and clinical chemistry laboratory measurements will be provided.

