## 2.5.2. Baseline

In general, the baseline measurement is defined as the closest measurement taken prior to or at the time of the first study agent administration date unless otherwise specified.

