### 7. SAFETY

Safety will be assessed by summarizing the incidence and type of AEs and examining changes in laboratory parameters (hematology and chemistry), vital signs, and suicidal ideation and behavior.

In all the safety analysis, subjects who were randomized and received at least 1 (partial or complete) dose of study agent administration will be included and analyzed according to the treatment they actually received, regardless of the treatment assigned at randomization. No formal statistical comparison is planned.

Depending on the safety data categories, the cumulative safety data will be analyzed through different study periods which include but are not limited to through Week 16 and through the whole study period as appropriate. Unless otherwise specified, tabular summaries of safety events for key study periods are in general presented as follows:

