#### **Summaries through Week 20 or through Week 40**

Safety data through Week 20 and through Week 40 will be summarized by treatment group defined as follows:

1. **Placebo → Guselkumab 100 mg:** all subjects who were randomized to placebo at Week 0, started treatment with placebo only, and later crossed over to receive treatment with guselkumab. Only the safety events/measurements from these subjects that occurred on or after their first administration of guselkumab 100 mg will be included in this group.
2. **Guselkumab 100 mg:** all subjects who were randomized to guselkumab 100 mg at Week 0 and received study agent with guselkumab 100 mg. All the safety events/measurements from these subjects that occurred beginning at Week 0 will be included in this group.

3. **Combined Guselkumab 100 mg:** all subjects as described above in the Placebo → Guselkumab 100 mg and the Guselkumab 100 mg groups.

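### The worst-grade laboratory summary and the grade 2 or higher listing do not use the baseline grade, so they cannot separate abnormalities present at entry from worsening on treatment

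*SAP*

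**What the plan says.** SAP Section 7 sets the aim for laboratory safety as "examining changes in laboratory parameters (hematology and chemistry), vital signs, and suicidal ideation and behavior", next to the incidence and type of adverse events.

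Section 7.2 then plans these laboratory outputs:

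- Grading: "Applicable laboratory results will be graded according to National Cancer Institute's Common Terminology Criteria for Adverse Events (NCI-CTCAE version 4.03").
- Summary: "The worst NCI-CTCAE will be summarized by treatment group".
- Listing: "A listing of subjects with 1 or more NCI-CTCAE toxicity grade" 2 or higher, for hematology and chemistry.
- Plots: "Box plots of laboratory measurements and change from baseline will be provided for selected laboratory analytes".
- A display of all laboratory reports for the safety analysis set.

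A baseline is available. Section 2.5.2 gives a general rule ("the baseline measurement is defined as the closest measurement taken prior to or at the time of the first study agent administration date unless otherwise", the closing words leaving room for exceptions), and Section 7.2 sets its own baseline for nonfasting glucose. Neither is applied to the toxicity grades.

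For the Week 20 and Week 40 summaries, Section 7 says of the guselkumab group: "All the safety events/measurements from these subjects that occurred beginning at Week 0 will be included in this group". Of the placebo-to-guselkumab group it says: "Only the safety events/measurements from these subjects that occurred on or after their first administration of guselkumab 100 mg will be included in this group". The third column combines these two. None of the three is a placebo column.

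**The concern.** A change in toxicity grade needs two grades, one before treatment and one after. The summary uses one. The listing is triggered by any grade 2 or higher result, whether or not the subject already had it. The box plots do use baseline, but only for selected analytes, and they show distributions of values rather than which subjects rose in grade.

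The SAP treats its other safety data differently. Adverse events have a treatment-emergent rule (Section 7.1), vital signs are summarized as change from baseline (Section 7.3), and the eC-SSRS gets a maximum post-baseline score and a shift table (Section 7.4.1). Laboratory grades have none of these.

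What is at stake is how a primary objective, safety and tolerability (Section 1.1), will be read. Through Week 16 there is a placebo arm, but of only 15 subjects, so a chance imbalance at entry can create or hide an apparent difference. In the Week 20 and Week 40 tables there is no concurrent placebo column against which to judge the entry component.

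**Working it through.** The SAP states no figure for laboratory abnormalities, so there is nothing to reproduce. The check has a reading of the text and an illustration of size.

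**1. Does the charitable reading remove the problem?** Suppose that worst means worst after baseline.

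- Subject A enters at grade 1 and stays at grade 1. Worst post-baseline grade: 1.
- Subject B enters at grade 0 and rises to grade 1. Worst post-baseline grade: 1.

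The two fall in the same cell, so the problem remains. An abnormality that resolves after entry is a separate case: it counts only if the Week 0 pre-dose sample is in the window. The Section 7 wording for the guselkumab group permits that but does not say so outright.

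**2. Size.** Inputs:

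- Arm sizes 60 and 15 (SAP Sections 1.2 and 1.4).
- Entry prevalence b of a graded abnormality that persists: 2% to 30%, assumed.
- New onset t among subjects normal at entry: 5%, assumed and equal in both arms.

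Formulas:

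- Tabulated rate = b + (1 − b)t
- Share present at entry = b / tabulated rate
- Newly abnormal, as a fraction of the arm = (1 − b)t
- Expected subjects counted from entry alone = 60b and 15b
- Chance imbalance at entry = the sum of Bin(x; 60, b) × Bin(y; 15, b) over all x, y with |x/60 − y/15| ≥ 0.10

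For b = 10%: the rate is 0.10 + 0.90 × 0.05 = 0.145, the entry share is 0.10/0.145 = 69%, newly abnormal is 0.90 × 0.05 = 4.5%, and the expected entry counts are 6 and 1.5.

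| b | Tabulated rate | Share present at entry | Newly abnormal | Entry counts (60 / 15) | P(entry rates differ by ≥10 points) |
|---|---|---|---|---|---|
| 2% | 6.9% | 29% | 4.9% | 1.2 / 0.3 | 3% |
| 5% | 9.75% | 51% | 4.75% | 3 / 0.75 | 13% |
| 10% | 14.5% | 69% | 4.5% | 6 / 1.5 | 29% |
| 20% | 24% | 83% | 4.0% | 12 / 3 | 43% |
| 30% | 33.5% | 90% | 3.5% | 18 / 4.5 | 49% |

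**3. After the fix.** Counting only new abnormalities, the same binomial sum with (1 − b)t in place of b gives a 10-point difference with probability 12% at b = 2% and 8% at b = 30%. For the unadjusted tabulated rate it is 20% and 50%. The remaining imbalance comes from the 15 placebo subjects, each worth 1/15 = 6.7 points.

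**The case against.** **Nothing is tested.** Section 7 plans no formal comparison of safety data, and laboratory grades carry no success criterion. This stands, and it limits the importance of the point. Even so, Section 7 says the Week 16 tables allow comparison between groups, so they will be read that way.

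**The SAP does not say that entry abnormalities count as on-treatment toxicity.** A reader might infer such a rule. The text does not support it: Section 7.2 never calls the worst-grade table treatment-emergent and fixes no layout. What can be said is that the baseline grade is not used in what is specified.

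**Baseline information is not missing.** All laboratory reports will be displayed, and with about 75 subjects a flagged case can be traced to its entry value. This is true, but it leaves the work to the reader and does not alter the summary table. The change-from-baseline box plots partly meet the aim in Section 7, for selected analytes and not by grade.

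**Randomization balances entry abnormalities.** It does so on average and through Week 16. It gives no help in the later summaries, which have no placebo column.

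**The prevalence is assumed.** This stands. At 2% the entry share is 29% and the imbalance probability 3%, so the effect is modest for analytes that are rarely abnormal. A reader might also take 5% as the rate that a corrected table would show for new abnormalities. Under the formula used here it is 4.9% down to 3.5% of the arm.

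**Conclusion.** The point holds as a weakness in descriptive reporting. As specified, the worst-grade summary and the grade 2 or higher listing cannot tell a persisting entry abnormality from worsening on treatment, and this does not depend on whether the Week 0 sample is included. It falls short of the aim in Section 7 of examining changes in laboratory parameters.

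The size depends on the analyte and on assumptions outside the SAP: persistence of every entry abnormality, 5% new onset, and 2% to 30% entry prevalence. From 5% prevalence upward, about half or more of the counted subjects were abnormal at entry.

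It would go too far to conclude that the trial's safety conclusion is invalid or that the tables must show a false signal. No test rests on them, entry values can be traced, and the Week 16 table has a randomized comparator. The change should be made, mainly for the Week 20 and Week 40 summaries.

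**What to change.** In Section 7.2, replace the worst-grade sentence with a shift table of baseline grade by worst post-baseline grade, for each analyte and treatment group, and identify the subjects whose grade rises above baseline. A shift table also keeps persistent entry abnormalities in view, so nothing is lost.

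Keep the grade 2 or higher listing in full. Add the baseline grade and mark which values are post-baseline.

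State which baseline the placebo-to-guselkumab group uses in the Week 20 and Week 40 tables. Section 2.5.2 as written points to the value before the first study injection, which for this group is placebo.

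The cost is SAP wording and one reshaped table. The plan already grades the results and defines a baseline, so no new data are needed.

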## 7.3. Vital Signs

Vital signs variables including respiratory rate, blood pressure (systolic and diastolic) will be measured at visits as per the time and events schedule in the protocol. Descriptive statistics of the observed value and change from baseline of the vital signs will be summarized by treatment group.

## 7.4. Other Safety Parameters

### 7.4.1. Suicidal Ideation and Behavior

The electronic Columbia-Suicide Severity Rating Scale (eC-SSRS) will be used as a screening tool to prospectively evaluate the potential of guselkumab to induce suicidal ideation and

behavior. The eC-SSRS defines five subtypes of suicidal ideation and behavior in addition to self-injurious behavior with no suicidal intent, and is a fully-structured subject self-report questionnaire, including standardized questions, follow-up prompts, error handling routines, and scoring conventions. The Screening version of the eC-SSRS will be conducted at Screening followed by the Since Last Visit version of the eC-SSRS at all other visits through Week 40.

The eC-SSRS will be performed during each evaluation visit according to the assessment schedule. The eC-SSRS will be performed at screening after signing informed consent, after the pre-SIAQ at Week 0, and before study agent administration, and as the first assessment for all post-baseline visits. The baseline is defined as the most severe/maximum eC-SSRS score at screening and Week 0.

In addition, potential suicide related adverse events including suicidal ideation, suicidal behavior excluding completed suicide, and completed suicide will be identified by the investigators and collected in the eCRF.

The following are eC-SSRS categories and have binary responses (yes/no). A “yes” response to any eC-SSRS category will be assigned a score as below:

**Suicidal Ideation (1-5)**

1 = Wish to be Dead

2 = Non-specific Active Suicidal Thoughts

3 = Active Suicidal Ideation with Any Methods (Not Plan) without Intent to Act

4 = Active Suicidal Ideation with Some Intent to Act, without Specific Plan

5 = Active Suicidal Ideation with Specific Plan and Intent

**Suicidal Behavior (6-10)**

6 = Preparatory Acts or Behavior

7 = Aborted Attempt

8 = Interrupted Attempt

9 = Actual Attempt (non-fatal)

10 = Completed Suicide

If no events qualify for a score of 1 to 10, a score of 0 will be assigned (0=“Negative result [no suicidal ideation or behavior]”). Higher scores indicate greater severity.

The summary for suicidal ideation and behavior will be based on the safety analysis set. Suicidal ideation and behavior will be summarized based on the most severe/maximum post baseline eC-SSRS outcome or AE of suicidal ideation, suicidal behavior excluding completed suicide or completed suicide through Week 16, Week 20, and Week 40 will be provided. In addition, frequency distribution of the most severe/maximum post baseline eC-SSRS outcome will be tabulated by treatment group through the same 3 time periods.

The maximum score assigned for each subject will also be summarized into one of three broad categories: No suicidal ideation or behavior, suicidal ideation, suicidal behavior. A shift table for change in categories of no suicidal ideation or behavior, suicidal ideation, and suicidal behavior from baseline through Week 16 will be presented, where the baseline category is based on eC-SSRS score and the post baseline is based on eC-SSRS or AE data.

## **8. PHARMACOKINETICS/PHARMACODYNAMICS**

### **8.1. Pharmacokinetics**

Blood samples for measuring serum guselkumab concentrations (pre-injection if it is an injection visit) will be collected from all subjects at scheduled visits as indicated in the time and events schedule in the protocol.

The PK analysis will be based on subjects who received at least 1 administration of guselkumab and had at least one evaluable PK blood sample. No imputation of missing concentration data will be performed, that is, data summaries will be based on the observed data.

All concentrations below the lowest quantifiable concentration in a sample or missing data will be labeled as such in the concentration data listings or Statistical Analysis Software™ dataset. Concentrations below the lowest quantifiable concentration in a sample will be treated as zero in the summary statistics. All subjects and samples excluded from the analysis will be clearly documented.

For analysis of serum guselkumab concentrations, descriptive statistics, including arithmetic mean, SD, median, interquartile range, minimum, and maximum will be calculated, where appropriate, by treatment group at each sampling time point. Serum guselkumab concentrations by baseline weight ( $\leq 90$ kg,  $>90$  kg) will also be summarized by treatment group overtime. The PK concentration data may be displayed graphically.

All summaries for serum guselkumab concentration will exclude data collected after subjects (1) did not receive a scheduled guselkumab administration within  $\pm 14$  days of the protocol scheduled dosing date, or those subjects who discontinued study agent, (2) received a partial, incorrect, or an additional guselkumab administration, (3) or have invalid sample data if the sample is taken after study agent administration or a concentration value falls outside the predefined range ( $\pm 10 \times \text{SD}$ ). Of note, serum guselkumab concentrations prior to the first of such events will be included in the summaries.

If needed, a population PK analysis using a nonlinear mixed-effects modeling approach will be used to characterize the disposition characteristics of guselkumab in the current study. Data may be combined with those from pivotal Phase 3 studies (CNTO1959PSO3001 and CNTO1959PSO3002) to support a relevant structural model. Details will be given in a population PK analysis plan and results of the population PK analysis will be presented in a separate technical report.

The effect of serum guselkumab concentrations on efficacy may be explored.

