### **2.3.3. Pharmacokinetics Analysis Set**

The PK analysis set is defined as subjects who received at least one injection of guselkumab and have at least one valid blood sample drawn for PK analysis.

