#### **4.4. Extent of Exposure**

The exposure data will be summarized through Week 20 and through Week 28. The number and percentage of subjects who receive study agent will be summarized by treatment group for the safety analysis set. Descriptive statistics will be presented for the following parameters:

- Number of injections
- Cumulative total dose

In addition, the study agent lots received by treatment, including matching placebo for active treatment will be summarized.

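### SAP Section 8.1 applies the truncation rule for dosing deviations to a single invalid PK sample, so as written a correctly dosed subject loses all later valid concentrations

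*SAP*

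**What the plan says.** The rule is in SAP Section 8.1 (Pharmacokinetics). It opens "All summaries for serum guselkumab concentration will exclude data collected after subjects" and then numbers three items:

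- Item (1): the subject missed the dosing window for a scheduled guselkumab administration, or discontinued study agent.
- Item (2): the subject "received a partial, incorrect, or an additional guselkumab administration".
- Item (3): subjects who "have invalid sample data if the sample is taken after study agent administration or a concentration value falls outside the predefined range", the range being plus or minus 10 SD.

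A clarifying sentence follows: "serum guselkumab concentrations prior to the first of such events will be included in the summaries".

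Two other places bear on what counts as a unit of exclusion. Earlier in Section 8.1: "All subjects and samples excluded from the analysis will be clearly documented". In Section 2.3.3, the PK analysis set requires that subjects "have at least one valid blood sample drawn for PK analysis". Section 8.1 also says that blood is drawn before the injection at injection visits, and that summaries are given by treatment group and time point, and by baseline weight category.

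**The concern.** Items (1) and (2) change what the subject is exposed to from then on. A concentration measured after a missed, partial or extra dose no longer reflects the planned regimen, so dropping later data is reasonable. Item (3) is different in kind. A tube filled after the injection instead of before it, or one implausible assay value, is a fault of one specimen. It does not alter the doses the subject goes on to receive, and the SAP gives no reason why later samples should be affected.

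Putting all three under the same lead-in means that a programmer who follows the text discards good data. A programmer who follows the probable intent discards one value. The two would produce different tables from the same database. PK with this device is a secondary objective (Section 1.1), so the descriptive tables are the direct output for that objective.

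**Working it through.** The SAP gives no figure to reproduce here. The check is a reading of the text, followed by a count of what each reading removes.

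**Step 1: apply the sentence to each item.**

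| Item | Type of event | Data before the event | The sample at fault | Data after the event |
|---|---|---|---|---|
| (1) dosing window missed, or discontinued | changes later exposure | kept | not applicable | excluded |
| (2) partial, incorrect or additional dose | changes later exposure | kept | not applicable | excluded |
| (3) invalid sample | fault of one specimen | kept | not assigned | excluded |

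For (1) and (2) the before/after split works, because the event is a dose and not a sample. For (3) the event is the sample. The lead-in excludes what comes after it and the clarifying sentence keeps what comes before it, so the faulty concentration falls under neither rule.

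**Step 2: look for text that overrides this for item (3).** The sentence on excluded subjects and samples is a duty to document exclusions. It does not say which exclusions apply. Section 2.3.3 decides who enters the PK analysis set. It does not say which concentrations of a subject in the set are summarised. The only sentence that addresses which concentrations stay is the clarifying one, and it covers the list without exception.

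**Step 3: count what is removed.** Let a correctly dosed subject have K scheduled samples, of which only number j is invalid.

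- Rule as written: the K − j later samples are excluded, all of them valid.
- Sample-level rule: 1 sample is excluded, the invalid one.

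With K = 6 (an assumption), a fault at sample 1, 2, 3, 4, 5 or 6 costs 5, 4, 3, 2, 1 or 0 valid samples under the rule as written, and none under a sample-level rule. The direction needs no assumption: for any pattern of faults, truncation never keeps more valid samples than sample-level exclusion. The total does need assumptions, because K and the rate of faults are not in the SAP.

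**Step 4: check whether both triggers in item (3) can occur.** A single value can lie at most (n − 1)/√n sample SDs from the mean of a set that includes it. At n = 60 this is 59/√60 = 7.6, and at n = 75 it is 74/√75 = 8.5. The bound first reaches 10 at n = 102. If the 10 SD range were computed from one visit's data with the suspect value included, the out-of-range trigger could not fire in this trial. Section 8.1 does not say how the range is set, so this is conditional. The mistimed-draw trigger does not depend on it.

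**The case against.** The strongest reply is that the sentence is too loosely built to have one strict reading. Item (1) already breaks the construction, item (3) changes tense, and a reading that drops good samples without clearly removing the bad one is unlikely to be what was meant. The references to excluded samples in Section 8.1 and to a valid sample in Section 2.3.3 both judge validity sample by sample, and the phrase about the first of such events fits dated dosing events better than a data-quality condition.

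Most of this stands as evidence of intent: sample-level handling is the likely aim. It does not remove the defect, because neither reference gives a rule for item (3), and the sentence that does speak to retention makes no exception for it.

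Two stronger readings are tempting, and the documents do not support them.

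- A reader might infer a definite loss of data. With K samples and independent faults at rate q, the expected share of valid samples lost is 1 − Σ(1 − q)^j / [K(1 − q)], summed over j = 1 to K. This runs from 2.0% (K = 5, q = 1%) to 15.9% (K = 8, q = 5%). Every input is assumed, and clustering of faults within subjects would change the result. These percentages say nothing about this trial.
- A reader might infer a further flaw from item (3) naming study agent where (1) and (2) name guselkumab, since study agent includes placebo (Section 4.4: "the study agent lots received by treatment, including matching placebo for active treatment will be summarized"). This is not a flaw. The pre-injection rule applies to all subjects at all injection visits, and a timing rule that ignores treatment is coherent in a blinded trial.

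**Conclusion.** The point holds as a minor drafting error in a stated analysis rule. As written, item (3) truncates a correctly dosed subject's concentration profile at one invalid sample and leaves the status of that sample open.

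Its reach is limited to the descriptive serum concentration summaries. The co-primary and major secondary tests do not use these data. Any population PK analysis is governed separately: "Details will be given in a population PK analysis plan". The size of the loss cannot be determined from the SAP. The conclusion rests on the wording of Section 8.1 and on the premise that a mistimed draw or a stray assay value does not change later exposure. It does not show that the sponsor chose to truncate on a bad sample; the text supports only that the written rule would do so.

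**What to change.** Split the sentence in Section 8.1. Keep the exclusion of data collected after the event, and the retention of data before it, for items (1) and (2) only. Add a separate sentence for item (3): only the affected concentration is excluded, and the subject's other valid concentrations, earlier and later, stay in the summaries.

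The cost is one or two sentences in the SAP and a small programming change, with no new data. It is best settled before the Week 20 database lock, since Section 2 plans PK analyses for both locks and Section 1.5.2 unblinds most of the sponsor after the first.
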